1.0 ADMINISTRATIVE INFORMATION AND PRINCIPLES OF CLINICAL STUDIES

1.1 Contacts and Responsibilities of Study-Related Activities

A separate contact information list will be provided to each site.

2.0 STUDY SUMMARY

Name of Sponsor: Takeda Pharmaceutical Company Limited	Compound: TVP-1012			
Title of Protocol: A Multicenter, Open-label, Long-term, Extension, Phase 3 Study to Evaluate the Safety and Efficacy of TVP-1012 at 1 mg in Early Parkinson's Disease Patients Not Treated with Levodopa (An extension study from TVP-1012/CCT-001)	IND No.: Not applicable	EudraCT No.: Not applicable		
Study Number: TVP-1012/OCT-001	Phase: 3			
Study Design: This is a multicenter, open-label, long-term, extension, phase 3 study to evaluate the safety and efficacy of long-term administration of TVP-1012 at 1 mg for another 26 weeks in patients with early Parkinson's disease who have completed the 26-week treatment period in the preceding TVP-1012/CCT-001 study. Among participants of the TVP-1012/CCT-001 study, those consenting to participate in this study prior to undergoing the tests, observations, and assessments at Week 26 of the treatment period (VISIT 8) in the preceding study, and fulfilling the eligibility criteria will be enrolled in this study. From the day after the VISIT 8 of the preceding study, subjects will receive TVP-1012 1 mg once daily for 26 weeks in an unblinded manner. The visit numbers in this study will be continued from the preceding study, and the study visit week will be counted from the start of the treatment period in the preceding study. Patients will make a total of 7 visits in this study, i.e., at Weeks 26, 29, 32, 36, 40, 46, and 52 of the treatment period, to undergo designated tests, observations, and assessments.				
Primary Objective: To evaluate the long-term safety of TVP-1012 (1 mg/day) in Japanese patients with early Parkinson's disease				
Secondary Objective: To evaluate the long-term efficacy of TVP-1012 (1 mg/day) in Japanese patients with early Parkinson's disease				
Subject Population: Japanese patients with early Parkinson's disease who have completed the 26-week treatment period in the preceding study				
Number of Subjects: Approximately 182 continued from the preceding study	Number of Sites: Approximately 55 sites (Same study sites as the preceding study)			

CONFIDENTIAL

Dose Levels: TVP-1012 (1 mg/day) once daily, either before or after breakfast (the timing of the dose must be the same as in the preceding study)	Route of Administration: Oral
Duration of Treatment: 26 weeks in total	Period of Evaluation: 26 weeks in total
Main Criteria for Inclusion: 
• The subject has completed the preceding study.• The subject has shown no safety issues during the study treatment in the preceding study, in the judgment of the investigator or sub-investigator.	
Main Criteria for Exclusion: 
• Subject has donated 400 mL or more of his or her blood volume within 90 days prior to the initiation of the investigational drug in this study.• The subject is required to receive any of the excluded medications or treatments.• The subject is required surgery or hospitalization for surgery during the study period.	
Main Criteria for Evaluation and Analyses: Primary endpoint 
• Adverse events (AEs) Secondary endpoints 
• Clinical laboratory test values, vital signs, electrocardiogram (ECG), and weight• MDS-UPDRS Part II + Part III total score	
Statistical Considerations: The analyses for this study will be performed using pooled data from the preceding study and this study, in principle, based on data obtained after administration of TVP-1012. [Analysis methods for the primary endpoint] The following analysis will be based on the safety analysis set. A treatment-emergent adverse event (TEAE) is defined as an adverse event whose date of onset occurs on or after the start of treatment period study drug in the preceding study. TEAEs whose date of onset occurs on or after the start of TVP-1012 will be coded using the MedDRA dictionary. The frequency distribution will be provided using the system organ class and the preferred term for each treatment group as follows: 
• All TEAEs• Drug-related TEAEs• Intensity of TEAEs• Intensity of drug-related TEAEs	

- TEAEs leading to study drug discontinuation
- Serious TEAEs
- TEAEs over time

Sample Size Justification:

In the preceding study, the planned number of subjects to be randomized was a total of 240 (120 per group) and the planned number of subjects evaluable for the primary endpoint (change in the MDS-UPDRS Part II + Part III total score from baseline to Week 26 of the treatment period (LOCF)) was a total of 220 (110 per group).

Since this study is a long-term extension study in patients with early Parkinson's disease who have completed the 26-week treatment period in the preceding study, considering the potential dropouts in the preceding study, approximately 182 subjects will be enrolled in this study.

In addition, considering the potential dropouts in this study and in the preceding study, it is estimated that 155 subjects will be treated with 1 mg of TVP-1012 for 26 weeks and 59 subjects for 52 weeks.

3.0 LIST OF ABBREVIATIONS

AE	adverse event
ALP	alkaline phosphatase
ALT	alanine aminotransferase
AST	aspartate aminotransferase
AUC	area under the curve
BUN	blood urea nitrogen
Cmax	maximum observed serum concentration
COMT	catechol- O -methyltransferase
CRO	contract research organization
CYP	Cytochrome P-450
FDA	Food and Drug Administration
GCP	Good Clinical Practice
γ-GTP	γ-glutamyl transpeptidase
hCG	human chorionic gonadotropin
ICH	International Conference on Harmonisation
INN	international nonproprietary name
INR	international normalized ratio
LDH	lactate dehydrogenase
MAO	Monoamine oxidase
MDS	Movement Disorders Society
MedDRA	Medical Dictionary for Regulatory Activities
MHRA	Medicines and Healthcare products Regulatory Agency
PDQ-39	The 39-item Parkinson's disease questionnaire
PMDA	Pharmaceuticals and Medical Devices Agency
PT	preferred term
PTE	pretreatment event
QOL	quality of life
SOC	system organ class
SUSARs	suspected unexpected serious adverse reactions
TEAE	treatment-emergent adverse event
UPDRS	unified Parkinson's disease rating scale
WHO	World Health Organization

4.0 INTRODUCTION

4.1 Background

Parkinson's disease is the second most common neurodegenerative disorder of the central nervous system after Alzheimer's disease. The prevalence of Parkinson's disease is estimated to be 100-150/100,000 in the Japanese population, mostly affecting elderly people with peak age in the late 50s to 60s [1]. A significant increase in the number of patients is expected as the population ages in the future.

The 4 major symptoms of Parkinson's disease are resting tremor, muscle rigidity (muscle stiffness), bradykinesia, and postural instability. These motor symptoms are suspected to occur due to damage or death of substantia nigra dopaminergic neurons in the midbrain, followed by a reduction in dopamine volume in the striatum.

The Japanese therapeutic guideline recommends initially treating motor symptoms of Parkinson's disease with levodopa or a dopamine agonist, in principle, and rich evidence with these drugs used as first-line therapy are available [2].

In clinical practice overseas, the efficacy of initial treatment with MAO-B inhibitors has been demonstrated in Parkinson's disease and the therapeutic algorithm recommends MAO-B inhibitors as the first-line treatment for mild Parkinson's disease in addition to levodopa and dopamine agonists [3][4]. In Japan, selegiline is one of the MAO-B inhibitors available but not approved for first-line treatment of Parkinson's disease. If clinical development of MAO-B inhibitors is promoted in Japan, treatment options for patients with mild or early Parkinson's disease may expand.

TVP-1012 (INN: rasagiline) is a MAO-B inhibitor without an amphetamine structure. In comparison with selegiline, TVP-1012 is characterized by (1) a 5 to 10-fold MAO-B inhibitory effect, and (2) easy drug management due to not having an amphetamine structure and not being designated as ingredient in narcotics. As of September, 2014, rasagiline has been approved in 53 countries in Europe, the United States, and East Asian countries as a monotherapy for early Parkinson's disease, and also as concomitant therapy with levodopa for Parkinson's disease. Currently, clinical development for TVP-1012 as monotherapy for early Parkinson's disease and as an add-on therapy to levodopa for Parkinson's disease is ongoing in Japan.

CONFIDENTIAL

Efficacy Summary

A thick black horizontal bar, likely a redacted section of text.

Safety Summary

CONFIDENTIAL

4.2 Rationale for the Proposed Study

Based on these results, this study was planned to evaluate the efficacy and safety of long-term extension administration with TVP-1012 in Japanese patients with early Parkinson's disease who have completed the preceding study (TVP-1012/CCT-001). The comprehensive evaluation of the efficacy and safety of TVP-1012 in early Parkinson's disease will be performed based on the results of this study, Study TVP-1012/CCT-001, and overseas clinical studies.

The clinical development of TVP-1012 as an add-on to levodopa for Parkinson's disease is ongoing in Japan. Currently, a Phase 2/3 study (TVP-1012/CCT-002) and a Phase 3 study (TVP-1012/OCT-002) are underway.

CONFIDENTIAL

5.0 STUDY OBJECTIVES AND ENDPOINTS

5.1 Objectives

5.1.1 Primary Objective(s)

- To evaluate the long-term safety of TVP-1012 (1 mg/day) in Japanese patients with early Parkinson's disease

5.1.2 Secondary Objectives(s)

- To evaluate the long-term efficacy of TVP-1012 (1 mg/day) in Japanese patients with early Parkinson's disease

5.2 Endpoints

5.2.1 Primary Endpoint

- Adverse events (AEs)

5.2.2 Secondary Endpoints

- Clinical laboratory test values, vital signs, electrocardiogram (ECG), and weight
- Movement Disorder Society-Unified Parkinson's Disease Rating Scale (MDS-UPDRS) Part II + Part III total score

5.2.3 Additional Endpoints

- MDS-UPDRS Part I total score
- MDS-UPDRS Part II total score
- MDS-UPDRS Part III total score
- MDS-UPDRS Part IV total score
- MDS-UPDRS tremor score
- MDS-UPDRS bradykinesia score
- MDS-UPDRS muscle rigidity score
- MDS-UPDRS individual score
- Parkinson's Disease Questionnaire-39 (PDQ-39) Summary Index scores for individual domain

6.0 STUDY DESIGN AND DESCRIPTION

6.1 Study Design

Patients will make a total of 7 visits in this study, i.e., at Weeks 26, 29, 32, 36, 40, 46 and 52 of the treatment period, to undergo designated tests, observations, and assessments.

[figure not shown]
This is a multicenter, open-label, long-term, extension, phase 3 study to evaluate the safety and efficacy of long-term administration of TVP-1012 at 1 mg for another 26 weeks in patients with early Parkinson's disease who have completed the 26-week treatment period in the preceding TVP-1012/CCT-001 study.

Among participants of the TVP-1012/CCT-001 study, those consenting to participate in this study prior to undergoing the tests, observations, and assessments at Week 26 of the treatment period (VISIT 8) in the preceding study, and fulfilling the eligibility criteria will be enrolled in this study. From the day after the VISIT 8 of the preceding study, subjects will receive TVP-1012 1 mg once daily for 26 weeks in an unblinded manner.

The visit numbers in this study will be continued from the preceding study, and the study visit week will be counted from the start of the treatment period in the preceding study.

This study will be conducted in the same study sites as those of the preceding study (55 sites) and the number of subjects to be enrolled in this study is estimated to be 182 subjects after considering dropouts in the preceding study.

Schematic of Study Design is included as Figure 6.a. A schedule of study procedures is listed in Appendix A.

V: VISIT

* Informed consent for this study must be obtained prior to tests, observations, and assessments at Week 26 of the treatment period in the preceding study. Those who consent to participate in this study and fulfilling the eligibility criteria will be enrolled in this study. Subjects will start dosing from the day after the VISIT 8.

Figure 6.a Schematic of Study Design

CONFIDENTIAL

6.2 Justification for Study Design, Dose, and Endpoints

6.2.1 Justification for Study Subject

To evaluate the safety and efficacy of long-term administration of TVP-1012 in Japanese patients with early Parkinson's disease, this study will target subjects who have completed the preceding study and were assessed as not demonstrating safety concerns in the opinion of the investigator or sub-investigator.

6.2.2 Justification for Study Design

This open-label, long-term extension study has a common study design that allows for the evaluation of long-term safety. This study was designed as an extension study following the preceding study, to collect pertinent data on long-term administration in an efficient manner.

See Section 13.3 for Sample Size Justification.

6.2.3 Justification for Dose Regimen

[REDACTED]

In the preceding study, 1 mg of TVP-1012 or placebo was administered for 26 weeks to evaluate the efficacy and safety of TVP-1012 1 mg.

In this study, the dose of 1 mg of TVP-1012 will be maintained for subjects treated with 1 mg of TVP-1012 in the preceding study, to evaluate administration at 1 mg for 52 weeks. In addition, subjects treated with placebo in the preceding study will be switched to 1 mg of TVP-1012 in this study, to evaluate administration at 1 mg for 26 weeks, for the purpose of evaluating a large number of subjects as much as possible.

[REDACTED]

CONFIDENTIAL

6.2.4 Justification for Treatment Period

Parkinson's disease is a progressive disease and long-term administration is anticipated when TVP-1012 is prescribed. Therefore, another 26-week extension of treatment was planned following the 26-week treatment in the preceding study to evaluate the long-term safety of TVP-1012 for 6 months and 12 months.

6.2.5 Justification for Endpoints

In this study, the long-term safety and efficacy of TVP-1012 following the preceding study will be evaluated. As the safety and efficacy will be evaluated in pooled data from this and preceding studies, the same endpoints used for the preceding study were set.

Safety evaluation is the primary objective of this study. Of the safety evaluation variables in the preceding study, the frequency of adverse events (AEs) will be used as the primary endpoint and clinical laboratory test results, vital signs, ECGs, and weight will be used for the assessment of secondary endpoints.

In addition, MDS-UPDRS Part II + Part III total score, which was the primary efficacy endpoint in the preceding study, will be used as a secondary endpoint. The efficacy endpoints in the preceding study other than MDS-UPDRS Part II + Part III total score will be set as additional endpoints.

6.3 Premature Termination or Suspension of Study or Investigational Site

6.3.1 Criteria for Premature Termination or Suspension of the Study

The study will be completed as planned unless one or more of the following criteria are satisfied that require temporary suspension or early termination of the study.

- New information or other evaluation regarding the safety or efficacy of the study medication that indicates a change in the known risk/benefit profile for the compound, such that the risk/benefit is no longer acceptable for subjects participating in the study.

- Significant violation of Good Clinical Practice (GCP) that compromises the ability to achieve the primary study objectives or compromises subject safety.

6.3.2 Criteria for Premature Termination or Suspension of Investigational Sites

A study site may be terminated prematurely or suspended if the site (including the investigator) is found in significant violation of GCP, protocol, or contractual agreement, is unable to ensure adequate performance of the study, or as otherwise permitted by the contractual agreement.

6.3.3 Procedures for Premature Termination or Suspension of the Study or the Participation of Investigational Site(s)

In the event that the sponsor, an institutional review board (IRB) or regulatory authority elects to terminate or suspend the study or the participation of an investigational site, a study-specific procedure for early termination or suspension will be provided by the sponsor; the procedure will be followed by applicable investigational sites during the course of termination or study suspension.

7.0 SELECTION AND DISCONTINUATION/WITHDRAWAL OF SUBJECTS

All entry criteria, including test results, need to be confirmed prior to the administration of the investigational drug.

7.1 Inclusion Criteria

Subject eligibility is determined according to the following criteria:

1. In the opinion of the investigator or sub-investigator, the subject is capable of understanding and complying with protocol requirements.
2. The subject signs and dates a written, informed consent form and any required privacy authorization prior to the initiation of any study procedures.
3. The subject has completed the preceding study (TVP-1012/CCT-001 study).
4. The subject has shown no safety issues during the study treatment in the preceding study, in the judgment of the investigator or sub-investigator.
5. A female subject of childbearing potential* who is sexually active with a nonsterilized* male partner agrees to use routinely adequate contraception* from signing of informed consent to 1 month after the last dose of the investigational drug.

*Definition of female subjects of chiledbearing potential is defined in Section 9.1.10.

Contraception and Pregnancy Avoidance Procedure and reporting responsibilities are defined in Section 9.1.11.

[Justification of Inclusion Criteria]

- 1, 2 : These criteria were set to include subjects who understand the objective of the study and will cooperate in the study conduct.
- 3 : This criterion was set as this study is designed to conduct with subjects who have completed the 26-week treatment period in the preceding study.
- 4 : This criterion was set in consideration of subject safety.
- 5 : This criterion was set in consideration of safety risk associated with pregnancy.

7.2 Exclusion Criteria

Any subject who meets the following criteria will not qualify for entry into the study:

1. The subject is an immediate family member, study site employee, or is in a dependant relationship with a study site employee who is involved in conduct of this study (e.g., spouse, parent, child, sibling) or may consent under duress.
2. Subject has donated 400 mL or more of his or her blood volume within 90 days prior to the initiation of the investigational drug in this study.
3. The subject is required to receive excluded medications or treatments.
4. If female, the subject is intending to become pregnant during, or within 1 month after the last dose of the investigational drug; or intending to donate ova during such time period.
5. The subject requires surgery or hospitalization for surgery during the study period.
6. The subject who, in the opinion of the investigator or sub-investigator, is unsuitable for any other reason.

[Justification of Exclusion Criteria]

- 1, 5 : These criteria were set as basic matters to conduct clinical studies.
- 2 : This criterion was set as basic matters to conduct clinical studies in consideration of subject safety.
- 3 : This criterion was set in consideration of efficacy evaluation and subject safety.
- 4 : This criterion was set to avoid the safety risk associated with pregnancy to pregnant woman and fetus.
- 6 : This criterion was set to exclude subjects with unknown factors which might influence the evaluation of efficacy.

7.3 Excluded Medications and Treatments

The list of excluded medications and treatments is shown in Table 7.a. Subjects must be instructed not to take any medications, including over-the-counter products, without first consulting with the investigator or sub-investigator.

Table 7.a Excluded Medications and Treatments

Medication/Treatment	Duration	Exception
Excluded Medication		
(1) selegiline	From VISIT 8 through VISIT 14, or the day of study site visit for early termination.	—
(2) pethidine, tramadol	From VISIT 8 through VISIT 14, or the day of study site visit for early termination.	—
(3) reserpine, methyldopa	From VISIT 8 through VISIT 14, or the day of study site visit for early termination.	—
(4) Other investigational drug	From VISIT 8 through VISIT 14, or the day of study site visit for early termination.	—
(5) levodopa containing drug		
(6) Dopamine agonist		
(7) amantadine	From VISIT 8 through VISIT 14, or the day of study site visit for early termination.	—
(8) Anticholinergic agent		
(9) COMT inhibitor		
(10) droxidopa		
(11) zonisamide	From VISIT 8 through VISIT 14, or the day of study site visit for early termination.	—
(12) istradefylline		
(13) Psychoneurotic agent (phenothiazine, butyrophenone, benzamide, Atypical antipsychotic drug)	From VISIT 8 through VISIT 14, or the day of study site visit for early termination.	Quetiapine may be concomitantly administered without change in dose regimen throughout the study if the drug has been continuously administered in the preceding study.
(14) Antinauseant with dopamine agonistic property	From VISIT 8 through VISIT 14, or the day of study site visit for early termination.	domperidone may be concomitantly administered without change in dose regimen throughout the study if the drug has been continuously administered in the preceding study.
(15) CYP1A2 inhibitor (including ciprofloxacin, enoxacin, fluvoxamine, zafirlukast)	From VISIT 8 through VISIT 14, or the day of study site visit for early termination.	—

CONFIDENTIAL

Medication/Treatment	Duration	Exception
(16) dextromethorphan	From VISIT 8 through VISIT 14, or the day of study site visit for early termination.	—
(17) Antidepressant	From VISIT 8 through VISIT 14, or the day of study site visit for early termination.	—
(18) St. John's Wort (including supplements)	From VISIT 8 through VISIT 14, or the day of study site visit for early termination.	—
(19) Narcotic analgesic agent (excluding \leq 1% of codeine, dihydrocodeine)	From VISIT 8 through VISIT 14, or the day of study site visit for early termination.	—

Excluded Treatment

(20) Neurosurgical intervention (Pallidotomy, Thalamotomy, deep brain stimulation)	From VISIT 8 through VISIT 14, or the day of study site visit for early termination.	—
(21) Transcranial magnetic stimulation	From VISIT 8 through VISIT 14, or the day of study site visit for early termination.	—

Medications/treatments for AEs during the study period may be administered, provided that these treatments do not deviate from the above range. If a drug listed above is chosen as routine medication after study completion, this medication should be administered following a reasonable interval as needed, based on the precautions for use for each drug.

[Justification of Excluded Medications and Treatments]

(1), (2), (18), (19)

These criteria were set to ensure the safety of subjects, in consideration of adverse drug reactions due to concomitant use.

(3), (13), (14)

These criteria were set since there is a possibility of worsening Parkinsonism, which may affect the efficacy evaluation of TVP-1012; however, some drugs may be used concomitantly, if these drugs do not affect the efficacy evaluation of TVP-1012.

(4)-(12), (20), (21)

These criteria were set because they could influence the evaluation of efficacy.

(15) This criterion was set due to the effect on the pharmacokinetics of TVP-1012, considering the metabolic pathway mainly via CYP1A2.

(16) This criterion was set to ensure the safety of subjects, in consideration of possibly elevating serotonin level due to concomitant use.

(17) This criterion was set to ensure the safety of subjects and to minimize the effect on the efficacy evaluation due to mutually potentiated pharmacological action with concomitant use.

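### Protocol 7.3, Table 7.a item (14) bars dopamine-agonistic antinauseants, which contradicts its own rationale; the word almost certainly should be *antagonistic*

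*Protocol*

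**What the plan says.** Table 7.a in Protocol 7.3 lists the drugs and treatments barred during the extension. One row reads "14) Antinauseant with dopamine agonistic property". It applies "From VISIT 8 through VISIT 14, or the day of study site visit for early termination", with an exception for domperidone that was already in continuous use in the preceding study and stays at an unchanged dose.

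The justification below the table takes items (3), (13) and (14) together: "These criteria were set since there is a possibility of worsening Parkinsonism, which may affect the efficacy evaluation of TVP-1012". Item (3) is reserpine and methyldopa. Item (13) is "13) Psychoneurotic agent (phenothiazine, butyrophenone, benzamide, Atypical antipsychotic drug".

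Dopamine agonists have their own row, item (6). It is justified with items (4) to (12), (20) and (21), on the ground that these could influence the efficacy evaluation. Worsening of Parkinsonism is not mentioned there.

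Three other provisions depend on the table:

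- Exclusion criterion 3 in Protocol 7.2: "The subject is required to receive excluded medications or treatments".
- The rule on treating adverse events in Protocol 7.3: "Medications/treatments for AEs during the study period may be administered, provided that these treatments do not deviate from the above range".
- The excluded-medication category of protocol deviations in SAP 1.1.7.1.

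**The concern.** The rule and its reason point in opposite directions. If the rule is applied as worded, it bars a kind of antinauseant for which the stated reason makes no sense and does not bar the kind that the reason describes.

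This matters because the table is an operative rule. Under Protocol 7.4, subjects may take other drugs only on the investigator's prescription or after consultation, apart from emergencies. The investigator's reading of Table 7.a therefore decides what is given. A literal reader could prescribe a dopamine-blocking antinauseant for an adverse event, and the deviation table would then not show it. The possible consequences are worse motor symptoms in that subject and a distorted MDS-UPDRS Part II + Part III score at the visits concerned.

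**Working it through.** No arithmetic applies. The check sets the relevant texts side by side.

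1. **The rule.** Item (14) turns on a dopamine *agonistic* property. The same word stands in the current text and in the appended Amendment 1 text, so a one-off slip in text extraction is unlikely.

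2. **The reason.** The justification for item (14) is possible worsening of Parkinsonism.

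3. **What the protocol says about dopamine.** Protocol 4.1 attributes the motor symptoms to loss of dopaminergic neurons, "followed by a reduction in dopamine volume in the striatum". It adds that the Japanese guideline "recommends initially treating motor symptoms of Parkinson's disease with levodopa or a dopamine agonist, in principle". On the protocol's own account, then, a dopamine agonist treats these symptoms. Steps 1 and 2 cannot both be right.

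4. **Which of the two is wrong.** Suppose *agonistic* were intended and the rationale were misplaced. Item (14) would then largely repeat item (6), and it would belong with items (4) to (12) under their rationale. It is placed instead with items (3) and (13), under the worsening rationale. Now substitute *antagonistic*. The stated reason, the grouping with (3) and (13), and the separate row for agonists all fit. The error therefore lies in the word, not in the rationale.

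5. **Whether it was corrected.** The Amendment 1 log in Appendix C revises items (15) and (17) of the same table and leaves (14) alone. The later log lists only an entry for Section 13.1.3. Neither corrects the word.

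6. **What the literal rule leaves open.** It leaves open any dopamine-blocking antinauseant that item (13) does not catch. Item (13) names the phenothiazine, butyrophenone and benzamide classes, but under the label of psychoneurotic agents. It closes part of the gap, and the documents do not say how much.

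7. **What is untouched.** The primary endpoint is adverse events, analysed in everyone who received TVP-1012. That set, the TEAE definition, the planned summaries and the sample size figures do not depend on item (14). The score that could be affected is a secondary endpoint, summarised descriptively with confidence intervals (Protocol 13.1.3; SAP 2.1.1.1 and 2.1.1.2).

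**The case against.** The strongest reply is that the section corrects itself. The rationale sits in the same section as the table, item (6) makes a literal item (14) almost redundant, and prescribing runs through an investigator who has that rationale to hand. Most neurologists would read the row as intended. This stands as a reason to rate the point low. It does not remove the point, because an exclusion list should not work only when its readers reverse a word, and classifying deviations needs a rule that can be applied as written.

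A second reply is that sites may not have worked from this English wording. In the later amendment log, the old and new texts for Section 13.1.3 are the same in English apart from emphasis, which would fit a change made only in a source-language original. That is inference, since the documents do not say the text is a translation. It is still a good reason to confirm against the source text before changing anything.

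A third reply is that no particular antinauseant has been shown to fall through the gap, and that the Handling Rules for Analysis Data, which are not among the documents, may deal with affected efficacy data. Both parts stand.

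A reader might go further and infer that dopamine-blocking antinauseants were in fact given, that the MDS-UPDRS results are biased, or that the safety conclusions are compromised. The documents support none of these. They show a wording that permits such use, not that it happened. A reader might also take the domperidone exception as proof of the intended meaning. That would rest on pharmacology the documents do not state, and the argument does not need it.

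**Conclusion.** The clash between item (14) and its rationale is established from the documents alone, with high confidence. That the replacement should be *antagonistic* is a very strong inference but not a documented fact, so the sponsor should confirm it.

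Severity is minor. The effect on conduct is a possibility only, and neither the number of subjects affected nor any shift in the MDS-UPDRS summaries can be estimated from the documents. The conclusion assumes that the English text shown carries the rule the sites were given.

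**What to change.** After the sponsor has confirmed the wording against the source text, change *agonistic* to *antagonistic* in Table 7.a item (14). Keep the domperidone exception and the joint rationale for (3), (13) and (14) as they are. Issue the change as an amendment or clarification memo, tell the sites, and notify IRBs as Protocol 15.1 requires. Section 14.2 is not the natural route, because it concerns changes that follow a medically unavoidable deviation at a site.

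At the data review before database lock (Protocol 13.1), check the recorded concomitant medications for dopamine-antagonist antinauseants, so that any use is known when the MDS-UPDRS summaries are read. Protocol 9.1.7 already requires all concomitant drugs to be recorded, and SAP 1.2.3 already tabulates them by Preferred Name, so no new data and no special deviation counting are needed.

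The cost is one word, a notice to approximately 55 sites with any IRB steps, and one look through existing data. The clarification of item (15) in Amendment 1 is a precedent for a change of this kind in the same table. No planned analysis changes.
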